Participants will receive a link to a dietary recall questionnaire (Intake24, <https://intake24.co.uk/>) via email the next morning after taking part in the study, which they will be prompted to complete before midnight that day. They will be asked to provide as much detail as possible on what they had for dinner, snacks, and drinks after the restaurant visit. Based on this information and salt values calculated by Intake24, we will estimate the total salt consumed by the participants for the rest of the day after the visit.

Other macronutrient intake

Total kcal, sugar, and saturated fat intake [i.e., other nutrients that are not the main warning focus] will be calculated based on the nutritional content of the order of the participant.

Additional measures

Food choice motives

The “health” subsection of the Food Choice Questionnaire (29) will be used to measure the extent to which health motives may influence participants’ food choices. The subsection consists of 6 items, e.g. “It is important to me that the food I eat on a typical day....is nutritious” answered on a 4-point Likert scale ranging from “Not at all important” to “Very important”. We will calculate the mean response for the six items.

Aim guessing

Participants are told that the study is about dining habits in restaurants. At the start of the post-meal assessments, participants will be asked what they think the aims of the study were (free text response). Any participant that guesses the study aims to be investigating the influence of food warning labels on food choice will be coded as being aware of study aims. One researcher will code awareness of aims ([name]) and a second researcher will independently verify the coding.

Study flow

Recruitment	
 - Participants will be recruited via online adverts, word of mouth, and an existing participant database maintained by researchers at the University of Liverpool. - A link to the screening questionnaire will be provided. (Appendix A) - Participants will be stratified by SEP, age, and sex. 				

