Reimbursement	
 - Participants will receive £25 which will likely cover their lunch costs and serve as an incentive for people from different SEP strata to participate. Participants will either (i) pay for their own meal at the restaurant and receive £25 via invoice or (ii) have their meal paid for by a researcher using a prepaid card; if this costs less than £25, they can request to receive the remaining amount via invoice, if this costs more than £25, they will need to pay the difference at the restaurant. 	

Statistical analysis

Participant characteristics

Participant characteristics will be presented overall and by experimental condition in a table. Data will include age, gender, ethnicity, highest educational qualification, employment status, BMI, frequency of eating OOH, and hunger. Continuous variables will be summarised as means and standard deviations, and categorical variables will be summarised as counts and percentages.

Measured variables

Primary

A linear regression will be used to assess differences between menu conditions in terms of PME. The between-subjects predictor will be label condition, and the dependent variable will be PME.

Highest education level (categorical: NQF level 4 or above, NQF level 3 or below) will be included as a covariate in the model to account for stratification (30). Health motives (continuous) will be included as a covariate as this may predict outcomes (e.g., health motivated individuals may be more likely to believe a menu with labels will change their behaviour) (30). Age and gender will also be included as covariates as previous work suggests that this can influence ratings of label PME and salt intake (13).

Descriptive analysis will be used to report (overall and by condition) participants' label awareness, salt awareness, perceived knowledge gain, perceived influence, and policy support (dichotomised into support/oppose). Logistic regressions will be performed to assess the odds of (i) being aware of the label, and (ii) being aware of the salt content of the meals in the labelled menu group, using the control menu group as the reference category. The same covariates as above will be included.

Secondary

Linear regressions will be performed to assess differences in menu conditions in terms of total salt purchase and total salt intake. The same covariates as above will be included.

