A logistic regression will be performed to assess the odds of selecting a high salt meal in the labelled menu group, using the control menu group as the reference category. The same covariates as above will be included.

As some participants are likely to bring guests to the restaurant and guest tables are the unit of randomization, there may be clustering for outcome variables (i.e., the variation in PME and/or salt purchase/intake may be partially explained by table). We will test for clustering effects by comparing the within-table variability for outcome variables to the between-table variability. We will use the likelihood ratio test to ascertain the difference in likelihoods between the two. If this is statistically significant ($p < .05$) then there is enough evidence to suggest that there is a clustering effect of table groups eating together. If there is evidence of clustering then we will perform a series of linear mixed model analyses, with label condition as an independent variable, and table group as a random effect for primary and secondary outcomes.

Exploratory analyses

Linear regressions will be performed to assess differences in menu conditions in terms of later salt intake, and intake of other macronutrients. This is to examine whether individuals engage in any compensatory eating behaviour after seeing the labels (e.g., they are aware that they consumed a

high salt meal and therefore reduce their salt intake later in the day), or whether intake of other macronutrients (e.g., calories) is impacted. Again, the same covariates as above will be included.

Sensitivity

Sensitivity analyses will be conducted to test if results are the same after removing any participants that correctly guess the aims of the study (i.e., the effect of salt warning labels on food choice, or similar). If many participants identify the study aims (e.g., > 25%) we will examine if study aim awareness status moderates any effects of labelling by including this as a covariate (categorical) in analyses. Any deviations in findings from the main analyses will be reported.

Missing data

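### Tables are randomised, but the 260 ignores table and the analysis includes it only after a significant pre-test; with within-table correlation, power near d = 0.35 falls and type I error modestly exceeds 5%

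*Combined protocol and SAP*

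**What the plan says.** Three parts of the combined protocol and SAP bear on this point.

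- **Design.** Recruitment allows each participant up to nine guests. The Intervention section and the Study flow table assign everyone at a table to the same menu. The clustering paragraph (Statistical analysis, Measured variables, Secondary) accepts that "guest tables are the unit of randomization, there may be clustering for outcome variables".
- **Sample size.** 260 participants (130 per condition) are said to give 80% two-tailed power at d = 0.35 for PME, salt purchased and salt intake, using between-subject ANOVAs. No ICC, table size or design effect is given.
- **Analysis.** The defaults are ordinary linear and logistic regressions with education, health motives, age and gender as covariates. A likelihood-ratio test at p < .05 then decides whether table matters: "If there is evidence of clustering then we will perform a series of linear mixed model analyses", with "table group as a random effect for primary and secondary outcomes".

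Two of the outcomes to which that linear fallback would apply are handled as follows: "A logistic regression will be performed to assess the odds of selecting a high salt meal in the labelled menu group" and "Logistic regressions will be performed to assess the odds of (i) being aware of the label".

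**The concern.** Randomisation by table is a fact of the design, not a hypothesis for the data to settle. Two things follow.

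1. If people who eat together answer or order alike, 260 diners carry less information than 260 independent people. The stated 80% power then does not hold.
2. A pre-test of table has little power when the ICC is small. When it is non-significant although tables are correlated, the label effect is tested with standard errors that are too small.

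Three drafting gaps go with this but do not add to its weight.

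- The fallback is a linear mixed model, although high-salt choice, label awareness and salt awareness are binary.
- Later salt intake and other nutrients are listed under Secondary outcomes but analysed under Exploratory analyses, where no table term is stated. It is unclear whether the pre-test covers them.
- The interim paragraph does not say whether its significance check accounts for table.

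**Working it through.** **Inputs from the documents:** 130 per condition, d = 0.35, two-sided alpha .05, 80% power and cited PME effects of d = 0.58 to 0.63 (Sample size); tables of 1 to 10 (Recruitment). **Assumptions:** ICC, mean table size, spread of table sizes, and the share of variance explained by the covariates (R²).

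**Step 1. Reproduce 260.** For independent individuals the noncentrality is d√(n/2) = 0.35 × √65 = 2.82. The noncentral t distribution on 258 df gives power 80.3%. With 129 per arm it is just under 80%, so 130 is the individual-level answer, with no room for clustering.

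**Step 2. Power under clustering.** With design effect DE, the effective n per arm is 130/DE. At DE 1.2 this is 108.3, the noncentrality is 0.35 × √54.2 = 2.58, and power is 72.7%. With covariates the effect becomes d/√(1 − R²), with 4 df removed.

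| DE | Power, d = 0.35, no covariates | Power, d = 0.35, R² = 10% | Detectable d at 80%, no covariates |
|---|---|---|---|
| 1.00 | 80% | 84% | 0.35 |
| 1.05 | 78% | 82% | 0.36 |
| 1.10 | 76% | 81% | 0.37 |
| 1.20 | 73% | 77% | 0.38 |
| 1.60 | 60% | 65% | 0.44 |

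The largest DE that keeps 80% power is 1.007 without covariates, 1.06 if they explain 5% of variance and 1.12 if they explain 10%. At d = 0.58 without covariates, power is 98.9% at DE 1.2, 95.7% at 1.6 and 90.7% at 2.0.

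For equal tables DE = 1 + (m − 1) × ICC, so tables of 3 with ICC 0.10 give 1.20. For unequal tables (truncated geometric on 1 to 10), the random-intercept model has effective DE = Σm / Σ[m/(1 + (m − 1)ICC)]. At mean 3 and ICC 0.10 this is 1.31.

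**Step 3. The planned two-stage rule under the null.** This was simulated with 130 diners per arm, no covariates and 80,000 runs per cell (Monte Carlo error about 0.08 points). The label test used REML with t on (tables − 2) df. The plan does not say whether the likelihood-ratio test uses ML or REML, or a cut-off of 3.84 or 2.71, so ranges span all four.

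| ICC 0.10 | Pre-test significant | Type I error, two-stage rule | Type I error, table always included |
|---|---|---|---|
| Mean 2, equal | 18–31% | 5.6–5.8% | 5.0% |
| Mean 2, unequal | 27–41% | 5.9–6.3% | 5.1% |
| Mean 3, equal | 30–46% | 5.9–6.4% | 5.0% |
| Mean 3, unequal | 40–56% | 6.2–7.0% | 5.2% |
| Mean 4, equal | 39–56% | 6.0–6.6% | 5.0% |
| Mean 4, unequal | 47–63% | 6.4–7.2% | 5.2% |

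- **ICC 0:** two-stage error is 4.8–5.0%, so there is no excess.
- **ICC 0.05, equal tables:** the pre-test is significant in 7–14% (mean 2) or 10–19% (mean 3); error is 5.4–5.6% and 5.6–5.8%.
- **ICC 0.20, mean 2 to 4:** the pre-test is significant in 60–96%; error is 5.2–6.0%.

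Four covariates explaining 10% of variance leave the pattern unchanged (mean 3, equal, ICC 0.10: 30–45% significant, error 6.0–6.4%). With those covariates and table always included, power at d = 0.35 is 80% (mean 2, ICC 0.05), 79% (mean 2, ICC 0.10), 76% (mean 3, equal, ICC 0.10) and 72% (mean 3, unequal, ICC 0.10).

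**Step 4. Exploratory regressions.** If the pre-test does not cover them, error at alpha .01 with ICC 0.10 is about 1.4% (mean 2, equal), 1.9% (mean 3, equal) and 2.8% (mean 3, unequal).

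**The case against.** The plan does not overlook clustering. It names tables as the unit of randomisation and pre-specifies a test and a random effect, so the dispute is only whether that effect is conditional. The excess error is small and shrinks once the ICC reaches 0.20, because the pre-test then usually triggers the mixed model. The study is powered for PME, where the cited effects leave ample margin, and it calls itself a pilot for food choice and salt intake. Tables may also be small, since the plan says only: "As some participants are likely to bring guests to the restaurant". At an assumed mean of 1.5 and ICC 0.10, the effective DE is about 1.09, which covariates explaining 10% of variance would absorb. Finally, 260 is a minimum. At 500, power at d = 0.35 and alpha .05 is 94.6% at DE 1.2 and 87% at DE 1.6.

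Most of this is right, and it keeps the point modest. It does not remove it, for three reasons.

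- The Sample size section claims 80% power at d = 0.35 for PME, salt purchased and salt intake. That claim needs negligible clustering or helpful covariates, and the plan assumes neither explicitly.
- Extension is conditional: the interim result must be non-significant with d of at least 0.25, and PME is then tested at 0.025. Allowing for that rule, overall PME power at d = 0.35 rises only from about 73% to 76% at DE 1.2, and from about 60% to 71% at DE 1.6.
- The two problems cover different ranges. The pre-test fails at low ICC; where it works, the power loss is largest.

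**Conclusion.** The concern holds and should be fixed. The 260 is an individual-level figure, and nothing elsewhere in the documents adjusts it for table or makes the table effect unconditional. Before covariate adjustment, 80% power at d = 0.35 needs a design effect of about 1.01 or less; covariates explaining 5% to 10% of variance raise that to about 1.06 to 1.12. The excess false-positive rate is about 0.6 to 2 points at ICC 0.10, smaller at 0.05 (equal tables) and 0.20, and absent at 0. The power and error figures depend on assumed ICCs and table sizes. The structural fault does not: a non-significant pre-test cannot show that the unit of randomisation may be ignored. The main PME conclusion is not threatened if the effect is near the cited 0.58.

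**What to change.** 1. Delete the likelihood-ratio pre-test. State that table is the unit of randomisation and is included in every between-condition analysis (primary, secondary, interim, exploratory and sensitivity), with the covariates already specified.
2. Use a random-intercept linear model for continuous outcomes. For high-salt choice, label awareness and salt awareness, choose in advance either a random-intercept logistic model or GEE with a small-sample correction; the first gives a conditional odds ratio and the second a marginal one. Controls see no labels, so few may report noticing one. Say what will be reported if the label-awareness model does not converge.
3. Report the ICC with its confidence interval for each main outcome. This will help plan a later trial.
4. In the Sample size section, state that before covariate adjustment 260 gives about 80% power at d = 0.35 at DE 1, 78% at 1.05, 73% at 1.2 and 60% at 1.6 (detectable d 0.38 at 1.2 and 0.44 at 1.6), and that covariates may recover a few points. Add that the 80% falls to about 78% to 79% when table is always fitted and the ICC is 0. For unequal tables, 1 + (size-weighted mean table size − 1) × ICC is a conservative DE (1.36 against 1.31 at mean 3, ICC 0.10).

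The cost is wording. Appendix D already records table number and group size, and no extra recruitment is proposed. If the true ICC is 0, always fitting table costs about 1 to 3 points of power at d = 0.35 (simulated 80.2% to 78.9% at mean 2, and 80.6% to 78.4% at mean 3), and intervals widen slightly.

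### If table clustering is found, the plan names only linear mixed models, which leaves the three binary outcomes without a suitable clustered analysis

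*Combined protocol and SAP*

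**What the plan says.** Under Statistical analysis, Measured variables, Primary: "A linear regression will be used to assess differences between menu conditions in terms of PME". For awareness, "Logistic regressions will be performed to assess the odds of (i) being aware of the label" and, second, of having been aware of the salt content of the meals. Under Secondary, linear regressions are planned for salt purchased and salt intake, and "A logistic regression will be performed to assess the odds of selecting a high salt meal in the labelled menu group". All of these models are adjusted for education, health motives, age and gender, either directly or by a sentence referring back to those covariates.

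The clustering paragraph under Secondary recognises that "guest tables are the unit of randomization, there may be clustering for outcome variables". In a parenthesis it illustrates this with PME and salt purchase or intake. It then says "We will use the likelihood ratio test to ascertain the difference in likelihoods between the two", with p < .05 as the trigger. If the test is significant, "we will perform a series of linear mixed model analyses, with label condition as an independent variable, and table group as a random effect". The sentence ends by applying this to the primary and secondary outcomes. No logit link is named, no exception is made for binary outcomes, and the reference back to the covariates is not repeated.

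Under Exploratory analyses: "Linear regressions will be performed to assess differences in menu conditions in terms of later salt intake, and intake of other macronutrients", again with the covariates. The Measures section lists these same outcomes under Secondary outcomes. The Sensitivity paragraph does not mention table.

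**The concern.** The point is which model is used once table is in the analysis, not when table should enter it. The fallback names one model family for outcomes of two kinds. An analyst who follows it to the letter would fit a linear model to yes/no data and report a difference in proportions where the plan otherwise gives odds ratios. An analyst who reads it as meant for PME and salt only would have no clustered model for the binary outcomes, although whole tables of up to ten people (a participant and nine guests) share a condition.

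The food-choice and awareness results are at stake. Food choice is also one of the two outcomes on which the interim decision rests, and the Sample size section expresses it there as odds. If effect measure and adjustment set both shift when table enters, a reader comparing clustered with unclustered results could not tell how much of any difference comes from clustering.

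**Working it through.** **1. The plan's own figure.** Inputs from Sample size: d = 0.35, two-tailed alpha .05, power 80%. Normal approximation: n per arm = 2 × (1.960 + 0.842)² / 0.35² = 128.1, rounded up to 129, or 258 in total. The t-test solution is 129.1, so 130 per arm and 260 in total, with power 0.803. The stated 260 reproduces and is not affected by this point.

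**2. Count of tested outcomes, by analysis heading.**

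| Outcome | Heading | Planned model | Binary |
|---|---|---|---|
| PME | Primary | linear | no |
| Label awareness | Primary | logistic | yes |
| Salt awareness | Primary | logistic | yes |
| Salt purchased | Secondary | linear | no |
| Salt intake | Secondary | linear | no |
| High-salt meal selected | Secondary | logistic | yes |

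Three of six are binary. If later salt, kcal, sugar and saturated fat are added, because Measures lists them as secondary, the count is 3 of 10. The number of binary outcomes affected is three either way.

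**3. The two readings of the fallback.**

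- Literal, from the closing words "table group as a random effect for primary and secondary outcomes": all three binary outcomes get a linear mixed model. The estimate is a difference in proportions. The model assumes constant residual variance, whereas the variance of a 0/1 outcome is p(1 − p): 0 at a rate of 0%, and 0.5 × 0.5 = 0.25 at 50%. Control menus carry no labels, and label awareness is coded from a free-text description of high salt or similar, so a control rate near 0% is plausible. The documents give no figure for it.
- Narrow, from the parenthesis naming PME and salt: the linear mixed model suits those outcomes, but the binary ones keep plain logistic regression with no allowance for table.

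**4. What the change of scale means for food choice.** Sample size cites OR = 0.65 from a meta-analysis. With control rate p0, the labelled-menu odds are 0.65 × p0/(1 − p0), and p1 = odds/(1 + odds). The control rates are assumptions.

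| p0 | p1 | p1 − p0 |
|---|---|---|
| 10% | 0.067 | -0.033 |
| 30% | 0.218 | -0.082 |
| 40% | 0.302 | -0.098 |
| 50% | 0.394 | -0.106 |
| 90% | 0.854 | -0.046 |

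In reverse, a difference of -0.10 is an OR of 0.44 at p0 = 20% (0.10/0.90 divided by 0.20/0.80), 0.67 at 50% and 0.44 at 90%. Neither scale can be read from the other without the arm rates.

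**5. Link to the interim rule.** The plan equates OR 0.65 with d = .24. This reproduces as |ln 0.65| × √3/π = 0.431 × 0.551 = 0.238. On the same conversion, the continuation threshold d = 0.25 is an OR of exp(−0.25 × π/√3) = 0.64. A linear mixed model coefficient cannot be set against that threshold directly.

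**6. Covariates.** If they were left out of the fallback, the cost for PME would be mainly precision. With covariates explaining a share R² of the variance (assumed), the residual SD is √(1 − R²). Normal-approximation power at d = 0.35 with 130 per arm is then 0.806 with no covariates, and 0.825, 0.845 and 0.884 at R² = 0.05, 0.10 and 0.20. These figures ignore clustering, so they show direction and rough size only; they are not the power of the mixed model.

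**The case against.** The strongest case for the plan is that much of this rests on what it leaves unsaid.

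- A reader might infer that the covariates are removed. The sentence calls label condition an independent variable, not the only one, and the PME model is introduced in the same way, with its covariates following in the next paragraph. The text supports saying that the covariates are not restated, and no more.
- A reader might infer that the odds ratios are withdrawn. The plan never says that the logistic regressions are dropped.
- A reader might infer that later salt and macronutrient intake stay unclustered. Measures lists them as secondary outcomes, so the fallback may cover them. The exploratory label makes this ambiguous; it does not settle it.
- A reader might take OR 0.65 as the planning value. It is background; the study is sized on d = 0.35 for PME.
- A linear model on 0/1 data is not necessarily an invalid test, and a difference in proportions can be converted to an odds ratio if the arm rates are reported.
- A logit-link model has its own trouble: if no control participant is coded as aware of the label, the odds ratio cannot be estimated by ordinary means.

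All of these stand, and they narrow the point. They do not remove it, because neither reading of the fallback gives the three binary outcomes a clustered analysis that yields the planned odds. The last one shapes the fix.

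**Conclusion.** The point holds in this limited form. For three of the six outcomes tested under the Primary and Secondary headings, the fallback either changes the effect measure or supplies no clustered model. Two further matters are unclear and not demonstrably wrong: whether the four covariates stay in, and whether later salt and macronutrient intake are covered.

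The size is modest. PME, the outcome on which the study is powered, already gets a suitable model family, and the sample size is unaffected. The harm falls on the food-choice and awareness results: a different scale, a poor fit if control awareness is near 0%, or standard errors that ignore table. The count follows from the text. The risk differences rest on assumed control rates, the power figures on assumed R² without clustering, and near-zero control awareness on the absence of labels from the control menu. The documents do not support the stronger conclusion that the planned test would be invalid.

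**What to change.** Replace the fallback sentence with wording to this effect:

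- PME, salt purchased and salt intake: linear mixed model with a random intercept for table.
- Label awareness, salt awareness and high-salt meal selected: a logit-link clustered model, either a logistic mixed model or a GEE with table as the cluster and small-sample-corrected standard errors. Name one in advance. The GEE odds ratio keeps the population-average meaning of the planned logistic regression, and the mixed-model odds ratio is conditional on table; either is acceptable.
- Label awareness, if control awareness is at or near zero: a penalised fit or a table-level comparison of proportions, with the choice and its trigger stated in advance.
- Education, health motives, age and gender stay as covariates in all the clustered regression models.
- The same table adjustment applies to later salt intake, macronutrient intake and the sensitivity analyses.

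The cost is a few lines of SAP wording and slightly more complex modelling in standard software. No new data are needed.

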If [yes], how would the salt label have influenced your choice? Response options: I would have avoided choosing a meal high in salt; I would have chosen a meal high in salt; Other (free text response)

Policy support

If the UK Government introduced policy requiring restaurant menu items high in salt to feature these labels, how would you feel?" Likert scale ranging from 1 – 5 anchored by "strongly oppose" and "strongly support".

Control: Same as above

Additional thoughts on label

"Please use this box to add any additional thoughts which you may have about the salt label" (open text response).

Control: Same as above

Secondary outcomes

Total salt purchased

Determined based on the total order of the participant, including food and drink. Prior to study commencement, all menu items will be sent for nutritional analysis to determine salt content/100g. Menu items will be weighed before being sent for analysis using kitchen scales (Vitafit VT706), so that specific salt content per serving can be calculated.

Labelled item selected

Determined based on whether the food item selected featured a high in salt warning label (yes = 1, no = 0).

Total salt consumed

Salt consumption will be determined from the order that the researcher takes and an estimation of the proportion of the meal that was consumed. The researcher will take a photograph before and after consumption and will estimate the percentage consumed component(s) of the meal, taking into account whether participants leave a proportion of all meal components or specific components (e.g., low salt or high salt components). Participants will also be asked whether they shared any of their meal with someone else. A random 10% selection of percentage estimates will be performed by a second researcher to measure reliability. Food consumption will then be calculated by subtracting an estimation of the proportion of the meal that was consumed (taking into account if any has been shared) from the food purchase.

Later salt intake

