We do not foresee missing data being a problem as when we design measures in Qualtrics all fields will require a response, and all data will be collected by a researcher during the restaurant visit. However, it is possible that some participants will not complete the online questionnaire to assess later intake after the restaurant visit. Any missing data for later nutrient intake will be imputed.

Multiple comparisons

The alpha will be set at .05 for primary and secondary outcome analyses. To adjust for multiple comparisons, the alpha for exploratory analyses alpha will be reduced to .01.

Sample size

The label in the present study (or a similar label) has not previously been tested in a real-world UK context, in terms of PME or food choice. A RCT examining the effects of 'high in' added sugar labels on PME found large effects ($d = 0.58 - 0.63$) (7). A meta-analysis on food labelling found a small effect ($OR = 0.65$, or $d = .24$) of warning labels in terms of reducing consumers' probability of selecting less healthy items (31). However, a RCT examining the effects of 'high in' sodium labels on salt (g) and 'high in' item choice found very small effects ($d = 0.03$ and 0.04 respectively) (9), but there are important methodological differences (e.g., menu size) between this study and the present study. The primary purpose of the present study is to examine PME, so we will therefore power the study for this primary outcome, but in doing so we will have reasonable power to detect small-medium effects for our secondary outcome (food choice).

In the present study, G power calculation indicates a minimum sample of 260 participants (130 per condition) will provide sufficient power (80%, two-tailed) to detect small-medium between condition effects ($d = 0.35$) of the salt warning label on PME, salt purchased, and salt intake using between-subject ANOVAs (as planned).

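### Later salt intake and other macronutrient intake are labelled secondary in Measures but exploratory in the analysis plan, so the alpha for four tests (most plausibly .01) is never stated outright

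*Combined protocol and SAP*

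**What the plan says.** The Measures section opens a block headed "Secondary outcomes". It contains total salt purchased, labelled item selected, total salt consumed, later salt intake and other macronutrient intake, and it ends only where "Additional measures" begins. Later salt intake is measured by next-day dietary recall, from which "we will estimate the total salt consumed by the participants for the rest of the day after the visit". The last entry in the block reads "Total kcal, sugar, and saturated fat intake [i.e., other nutrients that are not the main warning focus] will be calculated" from the participant's order. Measures has no exploratory heading.

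The Statistical analysis section groups the outcomes differently. Its Secondary part covers salt purchase, salt intake and the odds of choosing a high salt meal. The other two measures appear under Exploratory analyses: "Linear regressions will be performed to assess differences in menu conditions in terms of later salt intake", with the other macronutrients named in the same sentence.

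The Multiple comparisons section then states: "The alpha will be set at .05 for primary and secondary outcome analyses". The next sentence lowers alpha to .01 for exploratory analyses. Nothing says which classification prevails where the two sections differ.

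**The concern.** Alpha in this plan depends on the class of the outcome, and four tests (later salt, kcal, sugar, saturated fat) carry two class labels. A p-value of, say, .03 for later salt intake is significant if the Measures heading governs and not significant if the analysis heading governs. These tests are meant to show whether diners compensate later in the day and whether other nutrients shift, so they bear on how any salt result is read. A Multiple comparisons section exists to fix such thresholds before the data are seen.

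The class label also has a second effect. The rule that brings in a mixed model with table as a random effect, if clustering is found, is limited to primary and secondary outcomes. So the label also decides whether table clustering is handled for these four outcomes, although tables are the unit of randomisation.

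**Working it through.** **1. The passages side by side**

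| Place in the document | How the two measures are treated | Class implied |
|---|---|---|
| Secondary objectives | Not listed | Not secondary |
| Experimental design, outcome list | Not listed | Not secondary |
| Measures | Under Secondary outcomes | Secondary |
| Statistical analysis, Secondary | Not analysed there | Not secondary |
| Statistical analysis, Exploratory analyses | Analysed there | Exploratory |

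Measures is the only place that makes them secondary. Measures itself states no alpha; .05 is reached only by carrying its heading into the Multiple comparisons rule.

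**2. The plan's own sample size.** Inputs from the Sample size section are d = 0.35, 80% power and a two-tailed test; alpha .05 is from Multiple comparisons.

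n per arm = 2(1.960 + 0.842)² / 0.35² = 128.2, rounded up to 129, or 258 in total. The t-based calculation gives 129.1, rounded up to 130 per arm, or 260 in total. The stated 260 is reproduced, and 130 per arm is used in step 5.

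**3. Chance that the two readings disagree when there is no effect.** Under the null, one p-value falls between .01 and .05 with probability .05 − .01 = .04. For at least one of four:

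- perfectly correlated tests: 0.04, or 4%
- independent tests: 1 − (1 − 0.04)⁴ = 1 − 0.849 = 0.151, or about 15%

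Three of the four outcomes ("Total kcal, sugar, and saturated fat intake") come from the same order, so positive correlation is likely and 15% is the high end.

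**4. Chance of at least one false positive across the four tests, if independent**

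- at .05 each: 1 − 0.95⁴ = 18.5%
- at .01 each: 1 − 0.99⁴ = 3.9%

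**5. Observed differences that fall in the gap.** The critical standardised difference is z × √(2/130), where √(2/130) = 0.1240.

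- at .05: 1.960 × 0.1240 = 0.243
- at .01: 2.576 × 0.1240 = 0.319

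An observed difference between about 0.24 and 0.32 standard deviations is significant on one reading only. This assumes 130 independent participants per arm with complete data, and ignores the covariates and table clustering. The protocol itself expects some non-response on later intake.

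**The case against.** The strongest reply is that there is no real ambiguity. Multiple comparisons assigns alpha to analyses, and the regressions on these outcomes appear once, under a heading that calls them exploratory. The secondary objectives and the design outcome list omit them, and the Sample size section speaks of food choice as the secondary outcome. Headings in Measures are also loose: the primary block holds policy support, which is a secondary objective, and a free-text comments box.

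Most of this stands. It shows that .01 is the better-supported reading. It also rules out a stronger inference that a reader might draw, namely that the plan sets two thresholds for the same tests and leaves the authors free to choose once the results are known. Applying .05 would mean overriding the explicit label in the analysis section.

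The reply does not remove the inconsistency. The .05 rule is worded in terms of secondary outcome analyses, and a regression on an outcome listed as secondary fits that wording. Probable intent is not a stated rule.

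A reader might also size the problem by comparing power at d = 0.35 under the two alphas. The plan gives that effect size for PME, salt purchased and salt intake, and gives none for these four outcomes, so the comparison does not measure what is at stake here.

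**Conclusion.** The inconsistency is real and minor. Four tests are classed as secondary in one section and exploratory in another, and alpha follows the class. The intended value is most plausibly .01, but the plan should say so. The 4% to 15% range assumes that all four effects are null and runs from perfect correlation to independence. Neither the contradiction nor the fix depends on that range. The primary outcome, the sample size and the three secondary outcomes analysed as such are untouched.

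**What to change.** Make three edits:

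- In Measures, move later salt intake and other macronutrient intake out of the secondary block and under a new Exploratory outcomes heading.
- In Multiple comparisons, state that alpha .01 applies to these four tests.
- In the clustering paragraph, extend the table random-effect rule to these exploratory outcomes. Without this clause, the relabelling would confirm their exclusion from the mixed-model provision.

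The cost is a heading and two sentences, with no change to data collection or sample size. The statistical downside is lower power for these four tests than a .05 reading would give. The loss cannot be put as a figure, because the plan states no effect size for them, and nothing is lost relative to the reading that the analysis section already favours.
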